6.9.3 Labelling and shipment of biohazard samples

The Principal Investigator ensures that samples are labelled and shipped in accordance with the Laboratory Manual and the Biological Substance, Category B (materials containing or suspected to contain infectious substances that do not meet Category A criteria), see Appendix C of this Clinical Study Protocol 'IATA 6.2 Guidance Document'.

Any samples identified as Infectious Category A materials are not shipped and no further samples taken from the patient unless agreed with AstraZeneca and appropriate labelling, shipment and containment provisions are approved.

All archival tumour samples should be shipped at ambient temperature as per the Laboratory Manual to the AstraZeneca designated central Contract Research Organisation.

6.9.4 Chain of custody of biological samples

A full chain of custody is maintained for all samples throughout their lifecycle.

The Principal Investigator at each centre keeps full traceability of collected biological samples from the patients while in storage at the centre until shipment or disposal (where appropriate) and keeps documentation of receipt of arrival.

The sample receiver keeps full traceability of the samples while in storage and during use until used or disposed of or until further shipment and keeps documentation of receipt of arrival.

AstraZeneca keeps oversight of the entire life cycle through internal procedures, monitoring of study sites and auditing of external laboratory providers.

Samples retained for further use are registered in the AstraZeneca biobank system during the entire life cycle.

6.9.5 Withdrawal of informed consent for donated biological samples

If a patient withdraws consent to the use of voluntarily donated biological samples, then the samples will be disposed of/destroyed, and the action documented. If samples are already analysed, AstraZeneca is not obliged to destroy the results of this research. The patient may continue in the study.

The Principal Investigator:

- Ensures AstraZeneca is notified immediately of the patient's withdrawal of informed consent to the use of donated biological samples
- Ensures that biological samples from that patient, if stored at the study site, are immediately identified, disposed of/destroyed, and the action documented
- Ensures the laboratory(ies) holding the samples is/are informed about the withdrawn consent immediately and that samples are disposed of/destroyed, the action documented and the signed document returned to the study site
- Ensures that the patient and AstraZeneca are informed about the sample disposal

AstraZeneca ensures the central laboratory(ies) holding the samples is/are informed about the withdrawn consent immediately and that samples are disposed of/destroyed, the action documented and the document returned to the study site.

6.10 Anti-tumour activity

6.10.1 Tumour assessments

RECIST 1.1 guidelines for measurable, non-measurable, target lesions (TLs) and non-target lesions (NTLs) and the objective tumour response criteria are presented in Appendix F of this Clinical Study Protocol.

Baseline CT or MRI assessments of chest and abdomen (including liver and adrenal glands) must be performed no more than 28 days before the start of study treatment, and ideally

should be performed as close as possible to the start of study treatment. Additional imaging may be performed based on individual patient signs and symptoms. CT/MRI scan of the brain should be performed in patients with known or suspected brain mestastases.

The methods of assessment used at baseline should be used at each subsequent follow-up assessment. Follow-up assessments should be performed every 6 weeks (\pm 7 days) after the start of multiple dosing until objective disease progression as defined by RECIST 1.1 even if a patient discontinues treatment prior to progression.

Any other sites at which new disease is suspected should also be appropriately imaged. If an unscheduled assessment is performed and the patient has not progressed, every attempt should be made to perform subsequent assessments at the scheduled visits whilst the patient remains on study treatment.

Categorisation of objective tumour response assessment will be based on the RECIST 1.1 guidelines for response: CR (complete response), PR (partial response), SD (stable disease) and PD (progression of disease). Target lesion progression will be calculated in comparison to when the tumour burden was at a minimum (i.e. smallest sum of diameters previously recorded on study). In the absence of progression, tumour response (CR, PR, SD) will be calculated in comparison to the baseline tumour measurements obtained before starting treatment.

If the investigator is in doubt as to whether progression has occurred, particularly with response to NTLs or the appearance of a new lesion, it is advisable to continue treatment and reassess the patient's status at the next scheduled assessment or sooner if clinically indicated. If repeated scans confirm progression, then the date of the initial scan should be declared as the date of progression.

To achieve 'unequivocal progression' on the basis of non-target disease, there must be an overall level of substantial worsening in non-target disease such that, even in presence of SD or PR in target disease, the overall tumour burden has increased sufficiently to merit discontinuation of therapy. A modest 'increase' in the size of one or more NTLs is usually not sufficient to qualify for unequivocal disease progression status.

It is important to follow the assessment schedule as closely as possible. Please refer to the study plan in Section 6.1 and Appendix F, Section 4.1.

All RECIST 1.1 assessment images will be reviewed at site. Duplicates may be collected and stored by an AZ appointed representative, and sent for independent central RECIST 1.1 review, if deemed appropriate.

For the expansion cohort, the independent central RECIST 1.1 review will be conducted on all scans for all patients. Details of the independent central review will be documented in the Independent Review Charter.

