5.1.7 Duration of therapy

Patients should continue on treatment with AZD9291 until RECIST 1.1 defined progression or until treatment discontinuation criteria is met. There is no maximum duration of treatment as patients may continue to receive AZD9291 beyond RECIST 1.1 defined progression as long as they are continuing to show clinical benefit, as judged by the investigator.

If AZD9291 is discontinued for reasons other than disease progression, the patient must continue RECIST 1.1 assessments every 6 weeks until disease progression, even if further lines of anticancer therapy are administered.

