5.4.1 Procedures for discontinuation of a patient from investigational product

Once study medication is permanently discontinued it cannot be restarted.

A patient who discontinues study treatment is not always automatically withdrawn from the study. If a patient is withdrawn from study, see Section 5.4.3

Any patients who discontinue study treatment for reasons other than objective disease progression should have tumour assessments scans performed as scheduled in the protocol (see Table 2, Table 3 and Table 4 until objective disease progression is documented or death occurs, unless consent is withdrawn. Study procedure related SAEs and concomitant medication must be captured until the patient no longer has RECIST 1.1 assessments (disease progression or permanent withdrawal from the study).

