	Screening		ole Dose/(21 day cyc	-	Cycles 2-6 (21 day cycle)	Cycle 7 and every 6 weeks onwards	Discontin uation	28-day Follow up	Progress ion	Post progression survival F/U	Detail in section
Day	-28 to -1	D1	D8	D15	D1	D1				6 weekly relative to progression	
Tumour biopsy (optional)	X			Х			Х				6.8.1. 1
Vital signs	Х	X	Х	X	Х	Х	Х				6.3.3
Height	Х										6.3.3
Weight	X	Х			Х	Х	Х				6.3.3
Clinical chemistry /Haematology/Urinalysis	X	Х	X	Х	Х	Х	Х				6.3.5
ECG	Х	Х	Х	Х	Х	Х	Х				6.3.4
Echocadiogram/MUGA	Х	-	12 v	veekly rel	ative to first d	lose					6.3.7
PK blood sample (including metabolites)		Х	Х	Х	X (cycle 2 only)						6.6.1
Blood sample for cfDNA	Х	Х			6 wkly at RECIST visit X						6.8.1. 2
Genetic consent and blood sample (optional)	X										6.8.2
CSF (optional)		X (once only)								6.8.3	
RECIST assessments	Х	Every 6 weeks (relative to first dose) until progression)									6.10.1

Table 4Study Plan Phase II Extension Cohort

	Screening		ple Dose/C 21 day cyc	-	Cycles 2-6 (21 day cycle)	Cycle 7 and every 6 weeks onwards	Discontin uation	28-day Follow up	Progress ion	Post progression survival F/U	Detail in section
Day	-28 to -1	D1	D8	D15	D1	D1				6 weekly relative to progression	
Cognitive patient interview (optional)					4-0	6wks + 4-6 month	15				6.5.3
Dispense study medication		Х			Х	Х					5
Dose with AZD9291		-			Daily	v dosing					5
Concomitant medication	•										4.3.1
Adverse events											6.4
Survival										Х	6.3.8. 3

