7. EVALUATION AND CALCULATION OF VARIABLES AND STATISTICAL METHODS

7.1 **Definition of study endpoints**

To meet the objectives for this study, data for the following endpoints will be collected:

- Safety and Tolerability (Primary for escalation and expansion)
- AZD9291 pharmacokinetics (and metabolites AZ5104 and AZ7550) (Secondary)
- Pharmacodynamics (Secondary)
- Tumour response including ORR (Primary for extension, secondary for escalation and expansion), DOR, DCR and PFS (Secondary)
- Overall survival (Secondary for extension only)
- Pharmacodynamic markers in EGFRm+ T790M+ tumours at selected clinical doses (Secondary)
- Patient Reported Outcomes (Exploratory)
- Metabolite identification (Exploratory)
- Other biomarker data (Exploratory)
- Pharmacogenetics (Exploratory)
- Diagnostic tumour samples (Exploratory)
- For the extension cohort only, an independent central review (ICR) of the RECIST assessments will be used for the primary analysis of ORR and other RECIST-based outcomes.

Safety endpoints are defined in Section 6.4. Derivations, calculations and analysis plans for each of these endpoints are presented below.

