7.7.2 Progression Free Survival

PFS is defined as the time from date of first dosing until the date of objective disease progression as defined by RECIST 1.1 or death (by any cause in the absence of progression) regardless of whether the subject withdraws from AZD9291 therapy or receives another anti-cancer therapy prior to progression.

Patients who have not progressed or died at the time of analysis will be censored at the time of the latest date of assessment from their last evaluable RECIST assessment. If the patient has no evaluable visits or does not have baseline data they will be censored at 0 days unless they die within two visits of baseline.

If a patient discontinues treatment prior to progression and/or receives a subsequent therapy prior to progression then these patients will continue to be followed until evidence of objective disease progression as defined by RECIST 1.1 and their PFS time will be derived as defined above.

Note: Symptomatic deterioration will not be regarded as a progression event.

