4. TUMOUR RESPONSE EVALUATION

4.1 Schedule of evaluation

CT examinations of the chest and abdomen (including liver adrenal glands) will be used to assess tumour burden at baseline and follow-up visits. CT examination with intravenous contract media administration is the preferred method. MRI should be used where CT is no feasible or it is medically contra-indicated.

Clinical Study Protocol Appendix F Drug Substance AZD9291 Study Code D5160C00001 Edition Number 1 Date

Baseline tumour assessments should encompass all areas of known predilection for metastases in the disease under evaluation and should additionally investigate areas that may be involved based on signs and symptoms of individual patients and should be performed no more than 28 days before the start of study treatment. Follow-up assessments should be performed every 6 weeks (\pm 7 days) after the start of treatment until discontinuation of study treatment or withdrawal of consent. Any other sites at which new disease is suspected should also be adequately imaged at follow-up.

If an unscheduled assessment was performed and the patient has not progressed, every attempt should be made to perform the subsequent assessments as their scheduled visits. This schedule is to be followed in order to minimise any unintentional bias caused by some patients being assessed at different frequency than other patients.

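### Extension-cohort scans may stop at the site's call of progression while PFS and DoR are scored by central review, which biases both upward; the protocol's scan-stop rules also conflict

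*Protocol*

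**What the plan says.** **When scans stop.** Section 6.10.1 schedules follow-up imaging every 6 weeks "until objective disease progression as defined by RECIST 1.1 even if a patient discontinues treatment prior to progression". Table 4, the extension study plan, has "Every 6 weeks (relative to first dose) until progression". Section 5.4.1 keeps patients who leave treatment early on scans "until objective disease progression is documented or death occurs, unless consent is withdrawn". Appendix F Section 4.1 instead runs the same 6-weekly scans "until discontinuation of study treatment or withdrawal of consent". Section 6.10.1 itself refers the reader to that appendix section.

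**Who reads them.** Section 6.10.1 states that "All RECIST 1.1 assessment images will be reviewed at site", and Appendix F describes its scope as investigator assessment. Section 7.7 describes the ICR as two radiologists with adjudication, applied to all scans. It mentions no real-time read and no feedback to the site.

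**Who scores the endpoints.** For the extension, Section 7.1 says "an independent central review (ICR) of the RECIST assessments will be used for the primary analysis of ORR and other RECIST-based outcomes". Section 7.9 repeats this and adds the same analyses on investigator data as a sensitivity analysis.

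**Censoring.** Under 7.7.2, patients who have neither progressed nor died "will be censored at the time of the latest date of assessment from their last evaluable RECIST assessment". Death without progression is an event. DoR takes the PFS censoring time (7.7.3).

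**After progression.** Section 5.1.7 says "patients may continue to receive AZD9291 beyond RECIST 1.1 defined progression" while benefit continues. Section 6.3.8.3 follows extension patients every 6 weeks for survival, later therapy and unresolved AEs, with no imaging.

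**The concern.** Imaging can end on one reader's decision while the endpoint depends on another's. If the site calls progression and the ICR does not, the 6.10.1 rule produces no later scan on which the ICR could find it. Such patients have been judged by their physician to be progressing, so censoring them at that scan removes people at higher than average risk. The Kaplan-Meier estimate assumes that censored patients carry the same risk as those who remain.

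The cohort has a single arm, so no comparison group shares the bias and cancels it. DoR is the result that supports ORR in the primary report, and Section 5.5 times the full analysis so that responders can show durations beyond 6 months. Scans that were never taken cannot be recovered at the analysis stage.

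There is also an effect on ORR in the other direction. A partial response first seen by the ICR at the scan the site calls progression could not be confirmed under the 6.10.1 rule. This was not quantified.

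**Working it through.** No figure in the protocol depends on this point, so there is nothing to reproduce. The check compares the rules and then illustrates the size.

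**1. Rules side by side, for a patient with site progression but no ICR progression**

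| Patient | 6.10.1, Table 4 | Appendix F 4.1 |
|---|---|---|
| Stays on AZD9291 (5.1.7) | scans stop | scans continue |
| Stops AZD9291 at site progression | scans stop | scans stop |

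For a patient who stops treatment before any progression, the positions reverse: 6.10.1 and 5.4.1 continue scans and Appendix F 4.1 stops them. The passages contradict each other in both directions.

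**2. Inputs for the size**
- From the protocol: 6-weekly scans (42/30.44 = 1.38 months); at least about 8 months' follow-up (5.5); 175 patients.
- Assumed: site PFS exponential with median 10 months; a share q = 10%, 20% or 30% of site progressions not called by the ICR; in those patients ICR progression one or two scans later with equal chance; follow-up uniform from 8 to 16 months.

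**3. Ignoring deaths (closed form)**
Chance of no site progression per scan interval: s = exp(−ln 2 × 1.38/10) = 0.909. The last scan before 9 months is the sixth.
- Scans continued to ICR progression: (1 − q)s⁶ + q(s⁵ + s⁴)/2, with s⁶ = 0.563 and (s⁵ + s⁴)/2 = 0.651.
- Scans stopped at site progression, discordant patients censored: [1 − (1 − q)(1 − s)]⁶.

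| q | continued | stopped | difference |
|---|---|---|---|
| 10% | 57.2% | 59.8% | +2.6 |
| 20% | 58.1% | 63.5% | +5.4 |
| 30% | 59.0% | 67.3% | about +8.3 |

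Simulation with 200,000 patients per scenario agrees to within rounding and sampling error (59.7%, 63.5%, 67.1% against 57.1%, 58.1%, 58.8%). The median reads 12.4, 13.8 or 15.2 months against 11.0.

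**4. With deaths counted as 7.7.2 requires**
Adding an assumed 12-month median survival after site progression, simulation gives:

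| q | 9-month PFS bias | median, stopped | median, continued |
|---|---|---|---|
| 10% | +2.0 points | 11.0 | 11.0 |
| 20% | +4.1 points | 12.4 | 11.0 |
| 30% | +6.2 points | 13.4 | 11.0 |

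The largest median shift is 13.4 − 11.0 = 2.4 months. Most progressions fall on scan dates, so the median moves largely in steps of about 1.4 months and is a coarse measure here. For scale, the standard error of a 9-month PFS near 58% is about √(0.58 × 0.42/175) = 3.7 points.

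**5. Second set of assumptions**
True ICR median 6, 9 or 12 months, site call one or two scans earlier in 10% to 30%, 6 months' accrual, same survival after site progression. Six-month PFS is overstated in every scenario, from 72.5% read as 73.8% (+1.3) to 52.9% read as 59.5% (+6.6). The median moves by 0 to about 1.4 months. Of the discordant patients, 68% to 73% are censored and the rest become late death events.

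DoR was not simulated. It shares the end date and censoring time, so the direction is the same.

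**The case against.** **No further scans, even on treatment.** A reader might infer this from 6.10.1 and Table 4. Appendix F Section 4.1 contradicts it: a patient treated beyond progression keeps the 6-weekly schedule, and 7.7 sends all scans to the ICR. This objection stands. For these patients the defect is two conflicting rules, and which one sites follow is not settled.

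**All discordant patients censored just before their event.** This is also tempting, and the figures in step 3 assume it. Section 7.7.2 counts death without progression as an event and sets no missed-visit limit for patients with evaluable visits, and survival is checked every 6 weeks. The step 3 figures are therefore too large for this plan. The direction does not change, because death comes later than the unseen progression.

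**The assessor is not named.** This is true, and ICR operations are left to a charter that is not shown. That the site's call governs is an inference, but nothing in the protocol supports another reading.

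**The investigator analysis already covers it.** In part. In these simulations ICR progression never precedes the site's, so counting site progression as the event reproduces investigator PFS (about 56% at 9 months). The two differ only where the ICR calls progression first. The investigator analysis does not correct the ICR estimate.

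**In doubt, rescan.** Section 6.10.1 advises continuing and reassessing when the investigator is unsure. This lowers discordance but does not reach calls that the site makes with confidence.

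**Conclusion.** The point holds in limited form. Under 6.10.1, 5.4.1 and Table 4, extension imaging ends at a progression that the ICR need not share, and ICR-based PFS and DoR are then biased upward. Appendix F Section 4.1 would prevent this for patients still on treatment but contradicts the other passages. With deaths counted, 9-month PFS is overstated by about 2 to 6 points and the median by 0 to 2.4 months. That size rests on assumptions the documents do not supply: 10% to 30% discordance, a 10-month site median, ICR progression one or two scans later, and 12-month median survival after site progression. The upward direction held in every scenario run.

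PFS and DoR are secondary and descriptive, with no test, alpha or power attached. This is a worthwhile, cheap improvement. It is not a flaw that undermines the primary ORR analysis.

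**What to change.** 1. Reconcile 6.10.1, 5.4.1, Table 4 and Appendix F Section 4.1 into one rule. Patients who stop treatment early without progression stay on scans until progression. Extension patients still receiving AZD9291 after site progression stay on the 6-weekly schedule, with scans sent to the ICR, until ICR progression or end of treatment.
2. In 7.9, add a sensitivity analysis of ICR-based PFS and DoR that takes the earlier of ICR and site progression as the event. Present it as a conservative bound beside the planned investigator analysis, noting that the two coincide unless the ICR calls progression first.

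The cost is a few scans that Appendix F Section 4.1 already calls for, in patients still attending, and one extra analysis. Patients who stop treatment at site progression remain unscanned, so the bias is reduced and bounded, not removed.

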7. EVALUATION AND CALCULATION OF VARIABLES AND STATISTICAL METHODS

7.1 **Definition of study endpoints**

To meet the objectives for this study, data for the following endpoints will be collected:

- Safety and Tolerability (Primary for escalation and expansion)
- AZD9291 pharmacokinetics (and metabolites AZ5104 and AZ7550) (Secondary)
- Pharmacodynamics (Secondary)
- Tumour response including ORR (Primary for extension, secondary for escalation and expansion), DOR, DCR and PFS (Secondary)
- Overall survival (Secondary for extension only)
- Pharmacodynamic markers in EGFRm+ T790M+ tumours at selected clinical doses (Secondary)
- Patient Reported Outcomes (Exploratory)
- Metabolite identification (Exploratory)
- Other biomarker data (Exploratory)
- Pharmacogenetics (Exploratory)
- Diagnostic tumour samples (Exploratory)
- For the extension cohort only, an independent central review (ICR) of the RECIST assessments will be used for the primary analysis of ORR and other RECIST-based outcomes.

Safety endpoints are defined in Section 6.4. Derivations, calculations and analysis plans for each of these endpoints are presented below.

7.2 Determination of sample size

The primary objective of this study is to investigate the safety and tolerability and thereby identify the MTD, if possible, or maximum feasible dose of AZD9291 and to recommend dose(s) for evaluation in future clinical studies. Hence the number of patients in the cohorts has been based on the desire to obtain adequate tolerability, safety and pharmacokinetic and

Revised Clinical Study Protocol Drug Substance AZD9291 Study Code D5160C00001 Edition Number 3 Date

pharmacodynamic data while exposing as few patients as possible to the investigational product and procedures. Tumour response as measured using RECIST 1.1 will be assessed to provide preliminary anti-tumour activity in a patient population thought most likely to respond to AZD9291.

7.2.1 Dose Escalation Cohorts

For the dose escalation phase of the study, cohorts of 3-6 evaluable patients will be required. The total number of patients will depend upon the number of dose escalations necessary.

